**PROTOCOL COVER PAGE**

**REVISION HISTORY**

Revision #	Version Date	Summary of Changes	Consent Change?
1 (v2)	May 29, 2019	Response to reviewer concerns	Yes
2 (v2.01)	Aug 1, 2019	Addition of Safety Screen worded for Minors. No other change to protocol document.	No
3 (v2.02)	Aug 29, 2019	Clarified that no HIPAA data will be given to CMRR; corrected misloaded file documenting CMRR pre-approval for IRB review	No
4 (v3.0)	Nov 21, 2019	Added option for online consent for parent of “friend” via Redcap – changed in protocol and in Consent_Friend form; updated MRI screening form for minors per CMRR requirement; added additional self-report questionnaire measures for participant.	Yes (Consent_Friend form is updated to include option of online completion)
5 (v4.0)	Jan 28, 2020	Added option for research participants to complete questionnaires online using an iPad and Redcap.	No.
6 (v4.01)	Nov 11, 2020	Response to required modifications: Addition of clearer rationale for deception used in test procedures and indication that participants may withdraw their data and records when they are debriefed on this deception.	No
7 (v5.0)	Nov 30, 2020	Removed urine + oxytocin testing, added Certificate of Confidentiality language to consent form. Changes required for COVID safety and budget limits: added online consent and assent for all subjects, session 1 completely online, removed nurse exam, removed friend condition	Yes
8 (v5.01)	Jan 4, 2021	Made required changes: removed references to nurse exam from	No

## PROTOCOL TITLE: An MRI Study of Stress and Social Support

VERSION DATE: v.5.5 2022.09.20

		section 17.2 and removed references to involvement of a friend in section 13.1	
9 (v5.1)	Jan 15, 2021	Added video recording of sessions. Consent form updated to clarify recording.	Yes
10 (v5.2)	May 25, 2021	Added new NRI questionnaire version and contacting past participants to complete this addition, with payment of \$10 via online gift card or ClinCard.	
11 (v5.3)	Oct 27, 2021	Added recruitment method of contacting organizations through email.	No
12 (v5.4)	Aug 18, 2022	Added recruitment methods of mailing paper flyers and contacting people through organization listserv.	No
13 (v5.5)	Sep 20, 2022	Increased child payment to \$100 total and parent payment to \$50 total.	Yes

## **ABBREVIATIONS/DEFINITIONS**

- fMRI: Functional Magnetic Resonance Imaging
- MISTiC: Minnesota Imaging Stress Test in Children
- TSST: Trier Social Stress Test
- CORT, AUCi: salivary cortisol, area under the curve from intercept
- DHEA: dehydroepiandrosterone
- EKG: Electrocardiogram
- vmPFC: ventromedial prefrontal cortex
- ICD: Institute of Child Development

## 1.0 Objectives

### 1.1 Purpose:

The goal of this project is to examine the neural systems underlying the physiological responses to stress in children and adolescents, and to examine the effectiveness of various social partners (parent, stranger) in buffering youth from the physiological and brain effects of stress.

## 2.0 Background

### 2.1 Significance of Research Question/Purpose & Existing Literature:

Social buffering, a key concept in the psychobiology of stress, describes a phenomenon in which the presence and availability of social partners reduces activity of threat- and stress-mediating neurobiological and neuroendocrine systems (Gunnar, 2017). It is a key pathway through which social support reduces stress (Uchino et al., 2012) and enhances health (Kaplan et al., 1977). Impaired social buffering is a primary pathway through which adverse childhood experiences get under the skin to affect development (Hostinar et al, 2014). Despite its centrality to stress regulation, we know relatively little about the normative development of social buffering beyond the infant years.

### 2.2 Preliminary Data:

Prior behavioral data from our laboratories demonstrates that parents remain effective social buffers beyond infancy and throughout childhood. Among 9- and 10-year-olds, preparing for the Trier Social Stress Test (TSST) with a parent completely blocked elevations in cortisol to this social evaluative stressor (Hostinar et al., 2015). However, our results suggest that puberty results in a waning of parental HPA stress buffering effectiveness. Preparing for the TSST with the parent vs experimenter had no effect on 15- and 16-year-olds or on 11- to 14-year-olds who were at more advanced pubertal stages (Doom et al., 2016).

### 2.3 Study Aims:

The current study examines the neural response, as well as the cortisol hormonal response to social evaluative stress across the transition to puberty. We use a modified version of the Trier Social Stress Test (TSST) in the MRI scanner (called the Minnesota Imaging Stress Test in Children; MISTiC) to elicit social evaluative stress. In this project, we will randomly assign youth to complete this testing under one of three social buffering conditions: presence of a parent, presence of an experimenter (stranger), or no social support present (standard imaging condition).

The **long-term goal** of our research is to enrich understanding of stress regulation and its role in human development. The **overall objective** of this project is to understand normative processes in stress regulation and their neurobiological correlates as children leave childhood and become more autonomous in adolescence. The **central hypothesis** of this project is that early adolescence is a period of time when parental buffering wanes in efficacy, leaving many youth experiencing a relative dearth of relationships that can provide powerful stress buffers.

**The aim of the current study is to delineate changes in brain activation in response to social buffering by parents over the pubertal transition.**

**Hypothesis #1:** Parental social buffering will result in increased activation in brain regions associated with safety (e.g. vmPFC) and lower activation in brain regions involved in fear and pain (e.g., insula, amygdala, hypothalamus), as well as tighter coupling between the vmPFC and amygdala activity, but these relationships will wane with pubertal development.

**Hypothesis #2:** Neural activity associated with social buffering will mediate the effectiveness of physiological buffering by social partners.

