### **3.0 Study Endpoints/Events/Outcomes**

- 3.1 Primary Endpoint/Event/Outcome:  
Neural activity in vmPFC, insula, amygdala, and hypothalamus; salivary cortisol, heart rate, and respiration
- 3.2 Secondary Endpoint(s)/Event(s)/Outcome(s):  
Exploration of possible sex differences in different conditions later in puberty but not earlier in puberty.

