## 15.0 Statistical Considerations

*15.1 Data Analysis Plan:*

Preliminary Analyses to Determine Covariates Needed for Primary Analyses. The purpose of collecting data on potential covariates is to identify variables that are correlated with both the independent variable (social buffering condition, sex, pubertal stage) and the primary outcome measures. Those covariates that are associated with the independent and outcome variables will be controlled for in the primary analyses. Those that are not will be used to describe the sample, but will not need to be included in the analyses to obtain unbiased estimates. For each potential covariate, we will conduct correlations or t-tests with pubertal stage, and t-tests, ANOVAs, or chi-square tests (as appropriate) with sex and condition. If data do not confirm to modeling assumptions, we will use nonparametric analogs instead.

Preliminary Analyses of Imaging Data to Yield Primary Outcome Measures: fMRI data will be analyzed in FSL software (version 5.0.10) to generate voxel-wise contrast maps. Mean signal values will be extracted from these maps in a priori regions of interest for every participant using the methods described below. These preliminary analyses are used to generate the fMRI outcome variables of interest. The values of these outcome variables for each participant will be used in the general statistical analyses described in the next section. In total, these preliminary analyses will yield 6 primary task-related outcome variables, and 6 primary connectivity-related outcome variables.

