Task-based analysis: Math under social evaluative stress In first level analyses (single subject, single-run), math performance will be modeled for each participant using a voxel-wise multiple regression analysis with a task predictor (math trials vs. blank trials), 24 regressors for head motion (Satterthwaite et al., 2013) and additional regressors to model censored data points (motion spikes). In subsequent analyses, we will explore the utility of including other time varying individual differences variables (e.g., heart rate, respiration) that are known to contribute to the BOLD signal. However, since these measures are expected to vary by stress condition, removing the effects of these physiological variables may unintentionally remove effects of interest. Particular care will be taken to reduce the confound of head motion by censoring (identifying as artifact) any data point with absolute motion greater than 2 mm (1 voxel) or a framewise displacement greater than 0.5 mm, as well as the immediately preceding and following data points. Data points with DVARS values exceeding the

individual's 75th percentile plus two times the interquartile range will also be censored. Participants with more than 25% of data points censored for artifact will be excluded from further analyses.

Second level analyses (single-subject, multiple runs) will test the within-subject contrast of math performed with judges (social evaluative stress) relative to math performed alone (without social evaluation) to identify brain regions differentially activated by social evaluative stress. Based on prior literature, we will examine activation in 5 *a priori* regions of interest, including "pain-related" brain regions (dorsal anterior cingulate [dACC], left and right anterior insula) and "safety-related" or regulatory brain regions (ventromedial prefrontal cortex [vmPFC], and left and right dorsolateral prefrontal cortex [dlPFC]). For each subject, the mean percent change in MR signal (averaged across voxels) between judged math and math alone will be extracted from each of these 6 regions. This analysis will generate the 6 task-related brain activation outcome variables (listed in section 4.3) for each participant.

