Given that the MISTiC paradigm has not been used previously, it is possible that the most prominent regions of activity for this task may not match the *a priori* regions identified from the prior stress and social buffering literature. Therefore, we will also conduct an exploratory group-level analysis to identify primary regions of activation for the same socially evaluative math vs. non-evaluative math conditions (judged math vs. math alone, cluster corrected  $p < .005$ ). Because we expect that social buffering will alter the activity difference between social evaluative and non-evaluative math periods, we will use only the control condition (no social partner) to identify regions activated by this task. In the resultant group-level map, we will identify up to 4 primary regions of activation by selecting clusters that meet the cluster-corrected  $p < .005$  threshold, and then rank-ordering those regions by maximal z-statistic. Mean percent change in signal will be extracted for each participant (across all four buffering conditions) using anatomical masks derived from this analysis conducted in the control (no social partner) group. Therefore, exploratory analyses may generate up to 4 additional task-related MRI outcome variables.

Connectivity analysis: Speech preparation We are also interested in the neural correlates of anticipatory stress during the speech preparation period. However, the speech preparation period does not contain distinctive event markers needed for task-based fMRI analyses. Thus, to address the neural correlates of stress during speech preparation, we will use a seed-based connectivity approach to examine strength of functional connectivity between *a priori* seed regions of interest in the limbic system (amygdala, insula, hypothalamus) and target regions in the prefrontal

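### Hypothesis 1 gives amygdala and hypothalamus as example regions for lower activation, but neither is among the six prespecified task-activation outcomes; both serve only as connectivity seeds

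*Combined protocol and SAP*

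**What the plan says.** Section 2.3 states the aim: "The aim of the current study is to delineate changes in brain activation in response to social buffering by parents over the pubertal transition". It then sets out Hypothesis 1, which expects more activation in safety regions such as vmPFC, together with "lower activation in brain regions involved in fear and pain (e.g., insula, amygdala, hypothalamus), as well as tighter coupling between the vmPFC and amygdala", and expects these relationships to weaken with puberty. The fear and pain regions are introduced as examples.

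Section 3.1 gives the primary outcome as "Neural activity in vmPFC, insula, amygdala, and hypothalamus; salivary cortisol, heart rate, and respiration". This list has no such qualifier, but its term is neural activity, not activation.

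Section 15.1 announces "6 primary task-related outcome variables, and 6 primary connectivity-related outcome variables". In its task-based part, the pain-related regions are "dorsal anterior cingulate [dACC], left and right anterior insula", and the safety-related or regulatory regions are vmPFC and left and right dlPFC. Mean percent signal change "between judged math and math alone will be extracted from each of these 6 regions". In its connectivity part, bilateral amygdala and hypothalamus are the two seeds. Connectivity during speech preparation is compared with rest in three prefrontal targets.

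Section 15.1 also describes a data-driven map from the no-partner group: "exploratory analyses may generate up to 4 additional task-related MRI outcome variables". It names no region in advance.

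**The concern.** Hypothesis 1 makes an activation prediction and a coupling prediction, and gives three example regions for the first. The analysis plan turns only one of the three, the insula, into an activation outcome. Amygdala and hypothalamus are measured by a different quantity (connectivity) in a different part of the session (speech preparation).

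Section 15.1 explains why speech preparation is analysed by connectivity: that period has no event markers to model. The explanation does not carry over to the math task, where trials are modelled and activation is extracted. The documents give no reason for leaving these two regions out there.

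Followed as written, the plan can support or refute lower insula activation. It has no prespecified test of lower amygdala or hypothalamus activation. Any later activation result for either region, positive or null, would come from an added analysis or from the exploratory map, yet would look like an answer to a stated hypothesis.

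**Working it through.** **1. Reproduce the plan's counts (section 15.1).**

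- Task activation: dACC 1 + anterior insula 2 + vmPFC 1 + dlPFC 2 = 6, as stated.
- Connectivity: 2 seeds (bilateral amygdala, hypothalamus) × 3 targets (bilateral vmPFC, left dlPFC, right dlPFC) = 6, as stated.
- Neural outcomes in total: 6 + 6 = 12.

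**2. Set the regions named in Hypothesis 1 against those outcomes.**

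| Region | Activation outcome | Connectivity outcome |
|---|---|---|
| vmPFC | yes (1) | yes, as target |
| Insula | yes (2, left and right) | none in the final six |
| Amygdala | none | yes, 3 as seed |
| Hypothalamus | none | yes, 3 as seed |

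Amygdala or hypothalamus among the activation outcomes: 0 of 6. The predicted vmPFC-amygdala coupling is covered by the amygdala seed with the vmPFC target.

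**3. What is and is not fixed.** The contrast (judged math versus math alone) and the metric (mean percent signal change, averaged over voxels) are written down, and the exploratory outcomes use the same two. Both structures must be delineated anyway to serve as seeds. What is missing is a statement that they belong in the activation extraction, with which mask, and whether the amygdala is one bilateral outcome or two.

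**4. Cost of adding the two regions.** Bilateral amygdala plus hypothalamus takes task outcomes from 6 to 8 and neural outcomes from 12 to 14. Splitting the amygdala gives 9 and 15.

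Model: F test of the three-way interaction, numerator df u = 2, denominator df v = n − 24, noncentrality f²(u + v + 1), power .80. The 24 is an intercept plus 23 predictors, which is an assumption: 12 covariates + condition 2 + sex 1 + puberty 1 + two-way terms (2 + 2 + 1) + three-way 2.

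The plan's own figures first. At α = .05 this gives f² = .0548 at n = 200 (section 15.2 states .056) and .0709 at n = 160 (stated .070). The match is close but not exact. The setting u = 3, v = n − 4 comes nearer to the stated pair (.0556 and .0699), but u = 3 corresponds to four conditions, whereas the current design has three. The relative cost below does not depend on this difference in the baseline.

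Section 15.3 does not define the Benjamini-Hochberg family, so several are shown, each at the strictest step, α = .05/m:

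| Family | m | α | Detectable f², n = 200 | Detectable f², n = 160 | Power at the old detectable f² |
|---|---|---|---|---|---|
| Neural + cortisol + heart rate | 14 to 16 | .0036 to .0031 | .0952 to .0972 | .1237 to .1264 | .788 |
| Neural only | 12 to 14 | .0042 to .0036 | .0929 to .0952 | .1207 to .1237 | .786 |
| Task only | 6 to 8 | .0083 to .0063 | .0824 to .0867 | .1070 to .1127 | .772 |
| Task only, amygdala split | 6 to 9 | .0083 to .0056 | .0824 to .0885 | .1070 to .1150 | .760 |

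The power figures agree at both sample sizes to within .001, and also with 21 or 28 predictors in place of 23.

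**The case against.** The strongest reply is that nothing promised is left out. Hypothesis 1 speaks of a class of regions and offers these only as examples. Three of the six task outcomes (dACC and both insulae) test that class, and the one explicit amygdala prediction, coupling with vmPFC, has its outcome. This stands in part: the class is tested. But section 15.1 labels those three outcomes pain-related, and amygdala and hypothalamus, which the hypothesis itself names for lower activation, are the examples left out.

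A reader might go further and infer that section 3.1 declares a primary endpoint with no outcome behind it. The documents do not support that. Section 3.1 says neural activity, section 15.3 uses the same term for the brain dependent variables, and section 15.1 counts connectivity among the primary brain outcomes. On that reading each of the four regions in section 3.1 has at least one prespecified outcome.

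A reader might also infer that an activation analysis of these regions would be wholly improvised. It would not be: contrast and metric are set, and only inclusion, mask and laterality are open.

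Nor does the gap defeat Hypothesis 2. That hypothesis names no region, its mediation analysis is conditional on effects found first, and the connectivity outcomes for both structures remain candidate mediators.

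Finally, the exploratory map could select either region. It takes at most four clusters, ranked by z-statistic in the no-partner group, so it guarantees a test of neither. The sponsor may also have had reasons in the prior literature for the chosen six; the documents do not state them.

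**Conclusion.** The point holds as a narrow mismatch between Hypothesis 1 and the analysis plan. Of the three regions given as examples for lower activation, one (insula) has a prespecified activation outcome and two (amygdala, hypothalamus) do not; 0 of the 6 task outcomes cover them. Their connectivity is prespecified, three outcomes each. The finding rests on the wording of Hypothesis 1, which separates activation from coupling, and on the closed list of six regions in section 15.1.

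It should be fixed, because two regions named in the hypothesis have no prespecified outcome of the kind predicted. It does not threaten the validity of the other outcomes. The cost figures assume a 23-predictor model, numerator df of 2 and the strictest Benjamini-Hochberg step, with the family unknown.

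**What to change.** Choose one of the following and record it before any condition-level contrast is examined. The documents do not settle which is right.

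(a) **Add the regions.** Include bilateral amygdala and hypothalamus in the judged-math versus math-alone extraction, using the regions already needed as seeds. State the masks and whether the amygdala is one outcome or two. Task outcomes go from 6 to 8 and neural outcomes from 12 to 14 (one more of each if the amygdala is split). Count the additions in the Benjamini-Hochberg family, and define that family. This needs no new data, only two further mask extractions from contrast maps already produced. Power for an effect now detectable at 80% falls to about 79% in a family of all neural outcomes, with or without cortisol and heart rate. It falls to 77% in a task-only family, or 76% there with the amygdala split.

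(b) **Narrow the claim.** Restate Hypothesis 1 and section 3.1 so that amygdala and hypothalamus are connectivity outcomes only, and make no activation claim for them. This is a wording change, keeps 12 neural outcomes and costs no power.

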### **3.0 Study Endpoints/Events/Outcomes**

- 3.1 Primary Endpoint/Event/Outcome:  
Neural activity in vmPFC, insula, amygdala, and hypothalamus; salivary cortisol, heart rate, and respiration
- 3.2 Secondary Endpoint(s)/Event(s)/Outcome(s):  
Exploration of possible sex differences in different conditions later in puberty but not earlier in puberty.

### **4.0 Study Intervention(s)/Investigational Agent(s)**

- 4.1 Description: Note that there are no investigational agent(s) (e.g., drug, device) being evaluated. The study qualifies as an intervention due to random assignment into social buffering condition, to determine the effect of social partner on stress response.  
Child participants (11- to 14-year-olds) will be randomly assigned to one of three conditions during an fMRI version of a social evaluative stress paradigm: (1) no social buffer, (2) presence of experimenter/stranger, or (3) presence of a parent.
- 4.2 Drug/Device Handling: N/A
- 4.3 Biosafety: N/A
- 4.4 Stem Cells: N/A

## 5.0 Procedures Involved

5.1 Study Design: The study design is cross-sectional. 200 target children (11- to 14-year-olds) will be randomly assigned to one of three conditions: (1) no social support (standard MRI scanning condition); (2) presence of a stranger (experimenter); or (3) presence of a parent. Outcome measures will be compared across the three social buffering conditions. Pubertal stage will be included as a continuous variable in analyses of physiological and/or brain responses.

### Study Overview:

**Visit 1:** Parent and child will connect with a research staff member via video conferencing for a session lasting approximately 2 hours. Following a detailed overview of study and consent/assent procedures, participants will be asked to complete the following measures:

#### Parent:

- Questionnaire regarding family income, education level, and family composition
- Parent-report questionnaire about child's general health, behavior, and development (MacArthur Health Behavior Questionnaire; HBQ)
- Parent-report MRI safety screening questionnaire about the child to rule out any contraindications for MRI scanning

#### Children/adolescents:

- Questionnaire about general health, behavior, and development (MacArthur Health Behavior Questionnaire; HBQ)
- Questionnaire about their relationships with their parents and their best friend (Network of Relationships Questionnaire)
- Pubertal development questionnaire (Morris and Udry, 1980)
- Safety screening questionnaire to confirm safety in the MRI scanner

**Visit 2:** Parent and child will come to the Center for Magnetic Resonance Research for a session lasting approximately 2 hours. Following a session overview and consent/assent procedures, participants will be asked to complete the following measures:

